The study will take place over 3 years and consists of two phases. Phase 1 will involve using community-based participatory research (CBPR) to adapt the evidence-based GLB program to assure the needs of people with mobility impairment are appropriately addressed. Phase 2 will consist of a RCT to assess feasibility and effectiveness of the adapted GLB program on primary (i.e., weight and PA) and secondary health outcomes (i.e., waist circumference, upper arm circumference, BP, A1c, serum lipids, self-efficacy, function, and QOL). In Phase 2, 64 individuals (32 per group) with physical disabilities will be recruited via organizations that provide services to those with disabilities and randomized to an intervention group or a 6-month wait-list control group. To ensure the participation of 64 individuals, up to 75 eligible individuals will be consented. We expect to obtain sufficient participants to enroll everyone with the same start date, but if necessary, the study may be conducted among 3 cohorts with staggered start dates.

Phase 1. Adapting the GLB and assessing usability. We will use CBPR to adapt the GLB in iterative fashion guided by input from a 12-member **Advisory Board** comprised of community stakeholders. Members represent people with mobility impairment from the independent living community and scientists, plus health professionals. Board members will receive a small honorarium for their time.

The board will guide the team's efforts in adapting the GLB materials and content in year 1 and provide ongoing input and direction over years 2 and 3 as the team delivers the intervention and assesses its effects.

Phase 2. Assess feasibility and effectiveness of the adapted GLB for people with mobility impairment. A two-group (experimental and wait-list control), RCT will assess feasibility of delivering the intervention and its effectiveness on primary and secondary outcomes. Those assigned to the **control group** will wait 6 months before receiving the intervention. During the 6 month waiting period, the control group will be mailed monthly newsletters that address topics of making healthy lifestyle choices (achieve good sleep; reduce stress; spend time with friends; follow recommended schedule of vaccines & cancer screening; reduce risk of common conditions such as pain, depression; know your rights).

GLB intervention.

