 - 2) Invited to participate in teleconference-based group meetings, delivered in accordance with the GLB schedule and led by a trained lifestyle coach; meetings will be offered via a videoconferencing technology, such as Adobe Connect, which allows people to connect by landline, cell phone, tablet, or computer and connect either via audio alone or audio and video.
 - **3)** Invited to an optional in person meeting each month, during which participants can be weighed;
 - 4) Offered monthly individualized phone support from a lifestyle coach;
 - 5) Invited to include caretakers or key family support in meetings, if desired
 - **6)** Offered exercise aids that are appropriate for individuals with impaired mobility, including disability appropriate exercise DVDs, Garmin vivofit arm-based exercise trackers with heart rate monitors, pedal exercisers, and therabands (versus the GLB's offering of nonmodified exercise DVDs, pedometers, and other incentives). Participants will also be given Calorie

King™ calorie counting books, measuring cups, and a scale, in accordance with the mainstream GLB.

Conditions that may result in the subject exiting the study before the expected completion date include subject withdrawal of consent or decision not to continue their participation. Because of the remote nature of the intervention, participants may choose to continue the study despite adverse health events including hospitalization. However, participants will be explicitly advised to follow their doctors orders in all matters, including those most relevant to the study—physical activity and diet.

Outcome measures.

Feasibility measures will assess participants' adherence with key intervention components: **1)** group meeting attendance, **2)** individualized phone call attendance, and **3)** for the first 12 weeks only, self-monitoring of food intake and PA.

Effectiveness measures. **Primary outcomes** to assess the GLB effects will be collected at baseline and again at 3, 6, and 12 months. These will include participant's weight, PA, self-efficacy, function, and QOL. **Secondary outcomes** will be measured at baseline, 6, and 12 months and will include waist circumference, BP, A1c, serum lipids.

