Visits. Participants in the experimental group will be tested at baseline, 3 months, 6 months, and 12 months. Participants in the 6 month wait-list control group will be tested at baseline, 3 months, and 6 months, (for comparison to control group) and again at 9 months, 12 months, and 18 months (to assess intervention). Testing will be conducted in a private room at [name] research office at Baylor Institute for Rehabilitation Labwork will be processed at a UTSouthwestern lab, with

costs paid for by the study. All other testing will be performed by the PI, the trained program coordinator, or the trained research assistant. We estimate that the first visit will last approximately 1,5 hours, and each subsequent visit will last approximately 1 hour.

All visits (Baseline, 3 months, 6 months, 12 months):

- 1) Study staff will measure participants' weight using an accessible Seca scale (#676).(34) Weight for wheelchair users will be conducted first by measuring the total weight of the person in their wheelchair, the person will then transfer out of the chair to a mat table and those unable to transfer will be raised from their chair using a Hoyer lift, then the wheelchair will be weighed separately without the person in the chair. Patients who do not require a Hoyer lift but who do require assistance in transferring from their chair will to a mat table be assisted by study staff, who have been trained by physical therapists in performing transfer assists. The weight of the wheelchair will be subtracted from the total weight. Finally, staff will ask participants to report the use of any medications to control blood pressure or cholesterol, or any medications that may influence weight (such as certain medications to treat depression/anxiety, diabetes, or pain).
- 2) Participants will be asked to complete a pencil/paper questionnaire to measure self-reported physical activity (using the IPAQ short form), self-rated health abilities (SRAHP), quality of life (SF36E(35)), and to report on any change in medications that may influence weight, cholesterol, or blood pressure.

Baseline only:

- 1) Height will be measured with participants in a supine position when possible. Participants who have higher level injuries and/or difficulties in lying down will be asked to self-report their height.
- 2) Participants will be asked to complete a pencil/paper survey to gather demographic information; weight loss history; and history of common health complications.

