14. Biostatistics: We will use univariate analysis to summarize the measures of program usability and feasibility and examine their distributional properties (Aims 1 & 2). General/generalized mixed modeling analysis(41, 42) will be conducted for the primary and secondary effectiveness outcomes, to assess initial and sustained impacts of the adapted GLB intervention (Aim 3). More specifically, we will evaluate individual growth models for linear/nonlinear change from baseline to 6 months (level-1, time effects), overall group difference (level-2, group effect), and group difference in change (crosslevel, time-by-group interaction effect) (Hypothesis 3.1). Models will be adjusted for demographic variables (e.g. age, gender, ethnicity, disability severity, etc.), particularly if they are imbalanced after randomization, thereby providing more accurate estimates of the intervention impacts. We will also fit separate individual growth models for change from baseline to 12 months within both groups combined (time effects only) (Hypothesis 3.2). Our data will include missing observations due to either attrition or nonresponse. Intent-to-treat analysis will use restricted maximum likelihood estimation, which can produce unbiased estimates under the conditions of incomplete data. Subsequent intent-totreat analysis will utilize iterative Monte Carlo Markov Chain multiple imputation. (43) This approach includes all selected variables into the imputation process, which allows for greater recovery of the missing data.(44) All analyses will be performed using R(45) and SAS 9.3.(46) Secondary analyses will examine intervention effects for study completers who meet defined program adherence criteria.

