Sample size and power. Sample size was determined to provide sufficient power for our analyses on the primary outcomes. Previous studies showed that in general DPP translation efforts including the GLB yield large impacts on weight (median d = 0.99 at 3 months, 0.91 at 6 months, 0.74 at 12 months(16, 17, 19-21, 27, 47-49)) and relatively large impacts on PA (d = 0.69 at 3 months(20)). Results also indicated, at most, 16%, 23%, and 33% attrition at 3, 6, and 12 months, respectively. A sample size of 64 will allow greater than 90% power to detect a conservatively assumed group difference of 4% in weight change (95% power) and 80 min./week in PA (92% power). In the event of 33% attrition (the maximum observed in previous GLB studies), we will achieve 83-87% power to detect these differences. Thus, 64 participants (32 per group) will be enrolled.

References

- 8. Centers for Disease Control and Prevention. Physical activity among adults with a disability-United States, 2005. Morbidity and Mortality Weekly Report 2007;56(39):1021-1024.

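### The Hypothesis 3.1 growth model gives each randomised arm its own baseline mean; a common baseline mean would use data already collected and could sharpen the physical activity comparison

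*Combined protocol and SAP*

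**What the plan says.** Section 14 (Biostatistics) sets out the Hypothesis 3.1 analysis: "we will evaluate individual growth models for linear/nonlinear change from baseline to 6 months (level-1, time effects"), then "overall group difference (level-2, group effect), and group difference in change (crosslevel, time-by-group interaction effect"). On covariates it says "Models will be adjusted for demographic variables (e.g. age, gender, ethnicity, disability severity, etc.), particularly if they are imbalanced after randomization". Baseline PA and baseline weight are not named, and no equality of baseline means is stated. On estimation: "Intent-to-treat analysis will use restricted maximum likelihood estimation".

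The design in section 3 is a two-arm randomised comparison in which "64 individuals (32 per group) with physical disabilities will be recruited". The primary outcomes, weight and PA among them, "will be collected at baseline and again at 3, 6, and 12 months". PA is "self-reported physical activity (using the IPAQ short form"), according to section 4.

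The sample size paragraph gives 92% power for a PA difference of 80 minutes per week and 95% for a 4% difference in weight change. It also reports, from earlier work, "relatively large impacts on PA (d = 0.69 at 3 months(20"). It gives no SD, significance level, sidedness or correlation between baseline and follow-up.

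**The concern.** A free group term together with a time-by-group interaction leaves the two baseline means unconstrained, however time is coded. Hypothesis 3.1 is about greater improvement, so the tested effect is the difference between arms in change from baseline.

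In a randomised trial the expected baseline difference is zero. Estimating it freely means that chance differences at baseline are subtracted in full from the follow-up difference. When baseline predicts follow-up only moderately, which is plausible for a self-report activity questionnaire, full subtraction over-corrects and adds noise. Imposing one baseline mean lets the model correct only as far as the observed correlation supports. It is the mixed-model counterpart of analysis of covariance.

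What is at stake is precision on a primary outcome in a trial of 64 people, using a measurement that every participant already provides.

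**Working it through.** **The plan's own figures.** I assume a two-sided 5% level and a noncentral t with 2n − 2 degrees of freedom and noncentrality d√(n/2).

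- Weight: the cited 6-month d = 0.91 with 32 per arm gives 94.8%, in line with the stated 95%.
- PA: the stated 92% cannot be reproduced because no SD is given. By the normal approximation it implies d = (1.960 + 1.405) × √(2/32) = 0.841, so an SD of 80/0.841 = 95 minutes per week; solving the noncentral t gives d = 0.855.
- The earlier 3-month d = 0.69 gives 77.5% with 32 per arm. The plan does not equate this d with 80 minutes per week.
- With 33% lost (32 × 0.67 = 21.4 per arm), the d implied by 92% gives about 78%. The plan states 83-87% across the two outcomes, so its calculation may rest on a different contrast or treat partial data differently.

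**Variance saving.** Let r be the correlation between baseline and follow-up, σ the baseline SD and kσ the follow-up SD. Per participant, with complete data:

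- separate baseline means (difference in change): σ²(1 + k² − 2rk)
- common baseline mean: k²σ²(1 − r²)
- proportional saving: (1 − rk)² / (1 + k² − 2rk), which is (1 − r)/2 when k = 1

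At r = 0.5 and k = 1 this is 0.25/1.00 = 25%. At r = 0.5 and k = 1.3 it is (0.35)²/1.39 = 8.8%.

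| Assumed r | k = 1 | k = 1.3 | k = 1.5 |
|---|---|---|---|
| 0.3 | 35% | 19.5% | 12.9% |
| 0.4 | 30% | 14.0% | 7.8% |
| 0.5 | 25% | 8.8% | 3.6% |
| 0.6 | 20% | 4.3% | 0.7% |

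If the follow-up SD were smaller than baseline (k = 0.8), the saving would be 50-40%. For weight, an assumed r of 0.95 with equal SDs gives (1 − 0.95)/2 = 2.5%.

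**Does it carry over to a growth model?** For a linear model over visits at 0, 3 and 6 months, generalised least squares gives savings of 40-21% under compound symmetry and 36-20% under a first-order autoregressive structure, for r = 0.3-0.6. With random slopes (intercept and residual each half the baseline variance, six-month slope variance 0.1 to 1.0 times the baseline variance), the saving is 25-14%.

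**Simulation.** With 32 per arm, equal SDs and 20,000 runs per correlation, analysis of covariance had 34%, 24% and 18% less variance than change scores at r = 0.3, 0.5 and 0.6. Rejection rates under no effect were 4.9-5.1% for analysis of covariance and 4.6-5.1% for change scores.

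**Power for PA.** Divide d by √(1 − saving). Each range runs from r = 0.3 to r = 0.6.

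| Starting point | Planned contrast | Common baseline, k = 1 | Common baseline, k = 1.3 |
|---|---|---|---|
| Stated 92%, 32 per arm | 92% | 99-96% | 96-93% |
| Same d, 33% lost | 78% | 92-86% | 86-80% |
| d = 0.69, 32 per arm | 78% | 92-86% | 86-79% |

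All rows assume that the d refers to the difference in change.

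**The case against.** The planned model is standard, and four points against the concern have force.

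1. **Size.** A saving of 20-35% needs similar SDs at baseline and follow-up. The plan describes a less active population (section 2) coached progressively towards 150 minutes per week (sections 3 and 11). If uptake varies, the follow-up SD may well grow, and the saving could fall to a few percent. This stands.
2. **Starting power.** A reader might infer that PA has only 78% power and that this change rescues it. The documents do not support that. The plan powers PA on 80 minutes per week, and d = 0.69 is an earlier 3-month result. From the stated 92%, the gain is 4-7 points with equal SDs and 1-4 points at a ratio of 1.3.
3. **Model form.** Section 14 also allows generalised models and nonlinear change. If PA is analysed with a non-normal model, the normal-theory ratios do not carry over directly.
4. **Timing.** A common baseline mean is justified only if baseline is recorded before allocation is known. Section 9 places consent at the baseline visit, but the documents do not say when allocation happens, and PA is self-reported. This must be confirmed.

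Two further inferences should be resisted. One is that the plan will test for a baseline difference, or that its group term says nothing about the programme. Section 14 states no such test and no time coding; with time centred at month 6, the group term would be the month-6 difference. The other is that the planned analysis is biased or invalid. It is neither.

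The open-ended covariate list could admit baseline PA, but it does not specify it.

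**Conclusion.** The concern holds as a loss of efficiency on PA. Its direction is secure: in large samples, with the covariance adequately modelled, a common baseline mean does not increase the variance of the treatment contrast. Its size is uncertain, because the correlation, the SD ratio and the 5% two-sided level are my assumptions. For r = 0.3-0.6 and a follow-up SD 1 to 1.5 times baseline, the saving runs from about 35% down to about 1%. It matters most under attrition, and very little for weight. The change is worth making because it is nearly free, not because the planned test is wrong.

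**What to change.** In section 14, for the Hypothesis 3.1 models of weight and PA, specify a constrained longitudinal model: one common baseline mean for both arms, no group effect at baseline, and separate group effects at 3 and 6 months. Specify a covariance structure that lets the variance differ by visit, since an increase in PA variability is plausible. State when allocation takes place, and make the constraint conditional on baseline measures being recorded before it is known. Set this down before outcomes are compared by arm.

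The cost is a sentence or two of text and a small change to the model code. No extra participants, visits or data are needed.

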Baylor Institute for Rehabilitation Institutional Review Board

Protocol Template (for Investigator Initiated Studies)

Title: Group Lifestyle Balance Adapted for Impaired Mobility (GLB-AIM): Translating the GLB to Promote Healthy Weight in People with Mobility Disability (Impairment)

1. Introduction and Purpose:

This study will test **the effectiveness of the Group Lifestyle Balance**™ (GLB) program **adapted specifically for people with impaired mobility** using standard behavioral approaches for weight loss. The overarching aim of this study is to promote health and reduce chronic disease risk among people with mobility impairment by building an evidence base for weight loss. Our central hypothesis is that participants randomized to the intervention arm of the adapted GLB will show significant improvements on primary outcomes of weight and PA compared to a 6-month wait-list control group at 3 and 6 months, and will show improvements on several secondary health outcomes.

We propose the following specific aims and hypotheses:

Aim 1: To create an appropriate and usable adaptation of the GLB program for people with mobility impairment.

Hypothesis 1.1: Advisory board participants will identify key adaptations to make the GLB materials appropriate and usable for individuals with impaired mobility.

Aim 2: To establish whether the adapted GLB program for people with mobility impairment is a feasible intervention.

Hypothesis 2.1: Intervention participants will rate the program satisfactorily and attend at least 2/3rd of the weekly group-based meetings and monthly individualized phone calls. Lifestyle coaches will also rate the adapted program satisfactorily.

Aim 3: To determine if the GLB intervention adapted for those with mobility impairment is effective as determined by significant improvement in the primary and secondary outcomes in the intervention group compared to the wait-list control group at 3 and 6 months from baseline.

Hypothesis 3.1: The intervention group will demonstrate significantly greater improvements in our primary outcomes (weight and PA) than the wait list control group at 3 and at 6 months and will show significant improvements in secondary outcomes at 6 months.

Hypothesis 3.2: Both groups combined will demonstrate significantly greater improvements in the primary outcomes (weight and PA) after 3, 6 and 12 months of intervention and secondary outcomes after 6 and 12 months of intervention.

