Community-based interventions that can be delivered in group settings to people with mobility impairment may be particularly advantageous(10) given persistent transportation barriers.(11) Evidence that lifestyle intervention can lower risk for type 2 diabetes through weight loss and increasing physical activity (PA) has been demonstrated by the mainstream Diabetes Prevention Program (DPP). (12-15) The Group Lifestyle Balance (GLB) program,(16, 17) a direct adaptation of the DPP lifestyle intervention for group delivery in the community, has been shown to be effective in lowering weight and increasing PA in multiple community settings.(18-21)

To our knowledge, only three published studies have addressed weight loss interventions in individuals with physical disability(22-24). All of these support the use of lifestyle intervention as an effective means for encouraging weight loss. In 2014 the PI and program coordinator implemented a pilot study of the proposed research among a sample of 10 individuals with mobility impairments. Feasibility results showed that 70% participated in the program and these individuals attended an average of 79.3% of sessions and self-monitored more than half of the weeks. Usability results revealed high participant approval, with mean overall scores of 6.3±0.3 and 6.2±0.6 out of 7 on helpfulness and satisfaction scales, respectively. Program completers experienced a significant mean weight loss of 8.86±8.37 kg, or 7.4% of their start weight, and significantly reduced their BMI. These results compare favorably with those of the mainstream GLB and support further investigation.

The lifestyle changes the GLB recommends follow current national recommendations for physical activity by the American College of Sports Medicine/American Heart Association (ACSM/AHA)(25) and dietary recommendations follow the US Department of Agriculture 2010 dietary guidelines.(26) Physical activity recommendations suggest everyone, including those with disabilities who are capable, should engage in at least 150 moderate to vigorous physical activity each week. USDA dietary recommendations target healthy diet by reducing caloric consumption, increasing fruits/vegetables, and reducing consumption of saturated fatty acids, sodium, and cholesterol.

3. Concise Summary of Project:

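### The secondary analysis in adherent completers selects on behaviour that, in months 0–6, only the intervention arm can show; set against the wait-list, it is likely to favour the programme

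*Combined protocol and SAP*

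**What the plan says.** The main effectiveness analyses in Section 14 are intent-to-treat: mixed models fitted by restricted maximum likelihood, then multiple imputation. One further sentence follows: "Secondary analyses will examine intervention effects for study completers who meet defined program adherence criteria". Nothing else in the document specifies this analysis.

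Four other places bear on it:

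- **Meaning of effectiveness.** Aim 3 (Section 1) judges the outcomes "in the intervention group compared to the wait-list control group at 3 and 6 months from baseline".
- **What controls receive.** Under Phase 2 in Section 3, controls "will wait 6 months before receiving the intervention", and meanwhile "the control group will be mailed monthly newsletters that address topics of making healthy lifestyle choices".
- **What adherence is.** The feasibility measures in Section 3 are group meeting attendance, individual call attendance and, "for the first 12 weeks only, self-monitoring of food intake and PA".
- **The only threshold.** Hypothesis 2.1 expects intervention participants to "attend at least 2/3rd of the weekly group-based meetings and monthly individualized phone calls". It is a feasibility target and is not tied to the Section 14 analysis.

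**The concern.** All three adherence measures are parts of the intervention. During the randomised comparison a wait-list member has no session to attend, no coach call to take and no log to submit. An adherence criterion built on these measures can therefore be applied to one arm only. People who keep attending and logging may differ in motivation from those who do not, and motivation may affect weight whether or not the programme works. A contrast of adherers with the wait-list would mix that difference with any programme effect, yet the sentence would have it reported as an effect of the intervention.

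Two features raise the stakes. Section 2 already presents the pilot's weight loss among completers as comparing well with the mainstream programme and as support for further work. Section 1 says that results, if successful, will provide the framework for a large randomised trial. In addition, the criteria are called defined but are not defined anywhere, so the cut-off could be settled after results are known.

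**Working it through.** **Step 1. The plan's own figure, and the SD it implies.** Section 14 states 95% power for a 4% difference in weight change with 32 per group. It gives no SD, alpha or sidedness. Assuming two-sided 0.05 and a two-sample comparison of means:

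- d = (1.960 + 1.645) × √(2/32) = 3.605 × 0.25 = 0.90
- SD = 4 / 0.901 = 4.44 percentage points

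The d of 0.91 cited for 6 months gives 95.4% power, so the stated 95% is consistent with it. The plan states no figure for the adherence analysis.

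**Step 2. Assumed inputs.** The documents give neither of these:

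- The correlation r between adherence propensity and weight loss is taken as 0.3 to 0.5.
- The adherent share p is taken as 40% to 70%. The upper value is suggested by the pilot, where "70% participated in the program and these individuals attended an average of 79.3% of sessions". That is 7 of 10 people who took part, not a share meeting an adherence criterion.

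**Step 3. Spurious difference when the true effect is zero.** If adherers are the top fraction p on a standard normal propensity, their mean propensity is λ = φ(z)/p, where z is the cut-off:

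- p = 70%: 0.3477/0.70 = 0.497
- p = 50%: 0.3989/0.50 = 0.798
- p = 40%: 0.3863/0.40 = 0.966

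Against unselected controls the spurious d is r × λ. The smallest case is 0.3 × 0.497 = 0.15. The largest is 0.5 × 0.966 = 0.48 (0.485 in simulation).

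**Step 4. False-positive rates.** These come from a null simulation with 32 per arm, 40,000 trials per setting and a two-sided t-test at 0.05. Three control sets were used: all controls; a random 77%; and the most motivated 77%. The 77% reflects the 23% maximum 6-month attrition cited in Section 14. Each pair of values is for r = 0.3 and r = 0.5.

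| Adherent share | Spurious d, all controls | Weight, points (d × 4.44) | False positives, all controls | Random 77% | Most motivated 77% |
|---|---|---|---|---|---|
| 70% | 0.15, 0.25 | 0.67, 1.11 | 8.3%, 14.5% | 8.1%, 13.7% | 5.2%, 5.3% |
| 50% | 0.24, 0.40 | 1.07, 1.78 | 11.9%, 24.8% | 11.3%, 23.5% | 6.5%, 9.9% |
| 40% | 0.29, 0.49 | 1.28, 2.15 | 13.2%, 29.9% | 12.4%, 27.9% | 7.5%, 13.7% |

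Hand check of the first cell: 22.4 adherers against 32 controls give a standard error of √(1/22.4 + 1/32) = 0.275. Then 0.149/0.275 = 0.54, and Φ(−1.96 + 0.54) + Φ(−1.96 − 0.54) is about 8.4%, in line with the simulated 8.3%.

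**Step 5. Controls on the calculation.** With both randomised groups intact, the rate was 4.8–5.3% in every setting and the bias was zero. With r = 0 there is no bias under any comparator. If controls could be cut at the same propensity, the rate would also be about 5%, but the design gives no way to observe that propensity in them.

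**The case against.** The strongest reply is that the sentence names no comparator. A reader might infer that the plan commits to comparing adherers with the whole wait-list. The documents do not say so; that reading rests on Aim 3's definition of effectiveness. The analysis could instead be within-programme. Hypothesis 3.2 is modelled in both groups combined with time effects only, and wait-list members receive the programme after month 6, with testing at 9, 12 and 18 months. Both groups could then be filtered alike. This stands. It removes the asymmetry but not the selection, and it leaves no concurrent control to support a claim about the effect of the intervention.

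The size is also open to challenge. The sentence restricts to completers. If dropout removes the least motivated controls and 70% of the intervention arm adheres, the two selections nearly cancel and the false-positive rate is 5.2–5.3% (5.9% even at r = 0.7). This stands too, but the cancellation depends on why controls drop out and how many participants adhere, and it weakens at 40–50% adherent.

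Finally, the analysis is secondary and nothing assigns it a role in the effectiveness claim. That is correct and limits the consequence. It does not make the estimate unbiased.

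**Conclusion.** The point holds for this one secondary analysis. Adherence is behaviour after randomisation and, in months 0–6, is observable in one arm only. Under the Aim 3 contrast the estimate is likely to favour the programme. With no true effect and the assumed inputs, the spurious difference against all controls is about 0.15–0.49 SD. That is roughly 0.7–2.2 points of weight against a 4-point target, with a false-positive rate of about 8–30%. It falls to about 5–6% in the favourable case of 70% adherent and motivation-selected control completers.

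These figures rest on an assumed correlation, an assumed adherent share, an SD back-solved from the stated power, and a comparator inferred from Aim 3. They show a plausible range and do not predict this trial's result.

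A reader might go further and infer that the trial's effectiveness conclusion is compromised, or that the adherer result is bound to exceed the intent-to-treat one. The documents support neither: intent-to-treat is the main analysis and is untouched, and the bias is zero if adherence propensity is unrelated to weight change.

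**What to change.** - **Drop the biased contrast.** Do not report adherent participants against the wait-list as an effect of the intervention.
- **Describe instead.** Report outcomes by attendance among people receiving the programme, labelled descriptive, with a threshold fixed before analysis. The two-thirds attendance in Hypothesis 2.1 is one available choice.
- **If an effect in adherers is wanted,** add a complier-average estimate with randomisation as the instrument: the intent-to-treat difference divided by the share meeting the threshold, with its interval. It is zero when the intent-to-treat effect is zero. Present it as a supplement to intent-to-treat.
- **State its assumption.** It takes assignment to have no effect below the threshold. If partial attendance, materials or equipment help, it overstates the effect in adherers. For example, suppose 70% adhere with a 4-point effect and the other 30% gain half of that. The intent-to-treat effect is 0.7 × 4 + 0.3 × 2 = 3.4 points, and 3.4/0.7 = 4.86, which is 0.86 points (about 21%) too high.

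The cost is a rewording of the analysis plan and one extra, less precise estimate. Conduct, sample size and data collection do not change.
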